9.2.7 Expectedness

1274 For a serious adverse event that is considered possibly related to study device, the Medical
1275 Monitor will classify the event as unexpected if the nature, severity, or frequency of the event is
1276 not consistent with known risk information.

1277

9.2.8 Coding of Adverse Events

1278 Adverse events will be coded using the MedDRA dictionary. To facilitate coding, the clinical
1279 investigator will enter a preliminary MedDRA code which the Medical Monitor may accept or
1280 change (the Medical Monitor's MedDRA coding will be used for all reporting). The Medical

1281 Monitor will review the investigator's assessment of causality and may agree or disagree. Both
1282 the investigator's and Medical Monitor's assessments will be recorded. The Medical Monitor
1283 will have the final say in determining the causality as well as whether an event is classified as a
1284 serious adverse event and/or an unanticipated adverse device effect.

1285 **9.2.9 Outcome of Adverse Events**

1286 The outcome of each reportable adverse event will be classified by the investigator as follows:

1287 RECOVERED/RESOLVED: The participant recovered from the AE/SAE without sequelae.
1288 Record the AE/SAE stop date.

1289 RECOVERED/RESOLVED WITH SEQUELAE: The event persisted and had stabilized
1290 without change in the event anticipated. Record the AE/SAE stop date.

1291 FATAL: A fatal outcome is defined as the SAE that resulted in death. Only the event that
1292 was the cause of death should be reported as fatal. AEs/SAEs that were ongoing at the time
1293 of death; however, were not the cause of death, will be recorded as "resolved" at the time of
1294 death.

1295 NOT RECOVERED/NOT RESOLVED (ONGOING): An ongoing AE/SAE is defined as the
1296 event was ongoing with an undetermined outcome.

1297 An ongoing outcome will require follow-up by the site in order to determine the final
1298 outcome of the AE/SAE.

1299 The outcome of an ongoing event at the time of death that was not the cause of death, will be
1300 updated and recorded as "resolved" with the date of death recorded as the stop date.

1301 UNKNOWN: An unknown outcome is defined as an inability to access the participant or the
1302 participant's records to determine the outcome (for example, a participant that was lost to
1303 follow-up).

1304 If any reported adverse events are ongoing when a participant completes the study
1305 (or withdraws), adverse events classified UADEs will be followed until they are either
1306 resolved, or have no prospect of improvement or change, even after the participant has
1307 completed all applicable study visits/contacts. For all other adverse events, data collection will
1308 end at the time the participant completes the study. *Note: participants should continue to receive
1309 appropriate medical care for an adverse event after their participation in the study ends.*

1310 **9.3 Reportable Device Issues**

1311 All UADEs and ADEs as defined in section 9.1.1 will be reported on both a device issue form
1312 and AE form, except for skin reactions from CGM sensor placement or pump infusion set
1313 placement that do not require pharmacologic treatment. As noted in section 9.1.1, events that
1314 occur due to participant (user) error generally will not require completion of a device issue form.
1315 Such 'errors' could include improper use of an insulin pump or using a pump infusion set or
1316 CGM sensor for a period of time longer than its labeling.

1317 Device complaints and device malfunctions will be reported except in the following
1318 circumstances. These occurrences are expected and will not be reported on a Device Issue
1319 Form assuming criteria for a UADE or ADE have not been met:

1320 CGM sensor lasting fewer days than expected per manufacturer

1321 CGM tape adherence issues
1322 Battery lifespan deficiency due to inadequate charging or extensive wireless
1323 communication
1324 Intermittent device component disconnections/communication failures not requiring
1325 system replacement or workaround/resolution not specified in user guide/manual
1326 Device issues clearly addressed in the user guide manual that do not require additional
1327 troubleshooting

1328 **9.4 Timing of Event Reporting**

1329 SAEs possibly related to a study device or study participation and UADEs must be reported to
1330 the Coordinating Center within 24 hours of the site becoming aware of the event. This can occur
1331 via phone or email, or by completion of the online serious adverse event form and device issue
1332 form if applicable. If the form is not initially completed, it should be completed as soon as
1333 possible after there is sufficient information to evaluate the event. All other reportable ADEs and
1334 other reportable AEs should be submitted by completion on the on line form within 7 days of the
1335 site becoming aware of the event.

1336 The Coordinating Center will notify all participating investigators of any adverse event that is
1337 serious, related, and unexpected. Notification will be made within 10 days after the
1338 Coordinating Center becomes aware of the event.

1339 Each principal investigator is responsible for reporting serious study-related adverse events and
1340 abiding by any other reporting requirements specific to his/her Institutional Review Board or
1341 Ethics Committee.

1342 Upon receipt of a UADE report, the Sponsor will investigate the UADE and if indicated, report
1343 the results of the investigation to the sites' IRBs, and the FDA within 10 working days of the
1344 Sponsor becoming aware of the UADE per 21CFR 812.46(b) (2). The Medical Monitor must
1345 determine if the UADE presents an unreasonable risk to participants. If so, the Medical Monitor
1346 must ensure that all investigations, or parts of investigations presenting that risk, are terminated
1347 as soon as possible but no later than 5 working days after the Medical Monitor makes this
1348 determination and no later than 15 working days after first receipt notice of the UADE.

1349 Device malfunctions will be handled by the Sponsor or designee as described below. In the case
1350 of a CGM transmitter or sensor device malfunction, information will be forwarded to Dexcom by
1351 the site personnel, to be handled by their complaint management system.

1352 **9.5 Reporting to Novo Nordisk**

1353 For NovoLog: Copies of reports submitted to the FDA.

1354 For Fiasp:

- 1355 • Copies of reports submitted to the FDA.
- 1356 • All non-serious adverse events
- 1357 • All Serious adverse events
- 1358 • All events of pregnancy
- 1359 • All technical issues with the product alone, all technical issues with the combined
1360 system (pump and Fiasp) and all issues with the packaging material and labelling

1361 Prompt notification to Novo Nordisk of a SAE by the Coordinating Center will occur so that Novo
1362 Nordisk's legal obligations and ethical responsibilities towards the safety of participants and the
1363 safety of a trial product under clinical investigation are met. Novo Nordisk has a legal
1364 responsibility to notify both the local regulatory authority and other regulatory agencies about the
1365 safety of a trial product under clinical investigation. Novo Nordisk will comply with country-
1366 specific regulatory requirements relating to safety reporting to the regulatory authority, institution
1367 review board (IRB), independent ethics committee (IEC), and investigators.

1368 Drug related UADEs will also be reported to Novo Nordisk by the Coordinating Center within 15
1369 days of the Coordinating Center's first knowledge of the event. At a minimum, the following
1370 should be reported: Study name, Patient identification (e.g. subject number, sex, age), Event
1371 (Preferably diagnosis), Trial drug, Reporter, Causality, and Outcome.

1372 **9.6 Safety Oversight**

1373 The study Medical Monitor will review all adverse events and adverse device events that are
1374 reported during the study. SAEs typically will be reviewed within 24 hours of reporting.
1375 Other AEs typically will be reviewed on a weekly basis. Additionally, the Medical Monitor will
1376 review compiled safety data at periodic intervals (generally timed to the review of compiled
1377 safety data by the DSMB).

1378 The Clinical Study Director will be informed of all cases of severe hypoglycemia and DKA
1379 and the Medical Monitor's assessment of relationship to the study device; and informed of all
1380 reported device issues.

1381 A Data and Safety Monitoring Board (DSMB) will provide safety oversight. The DSMB will be
1382 informed of all cases of severe hypoglycemia and diabetic ketoacidosis irrespective of device
1383 relationship, all device-related SAEs, and all UADEs at the time that they occur during the study
1384 and will review compiled safety data at periodic intervals. The DSMB also will be informed of
1385 any ADEs not meeting criteria for a UADE if the Medical Monitor requests the DSMB review.
1386 The DSMB can request modifications to the study protocol or suspension or outright stoppage of
1387 the study if deemed necessary based on the totality of safety data available. Details regarding the
1388 DSMB's role will be documented in a separate DSMB document.

1389 **9.7 Stopping Criteria**

1390 In the case of an unanticipated system malfunction resulting in a severe hypoglycemia or DKA
1391 event (or a malfunction that could have led to severe hypoglycemia or DKA), use of the BP
1392 system will be suspended while the problem is diagnosed. The UADE will be reported to the
1393 IRB, DSMB, and FDA. After assessment of the problem and any correction, use of the system
1394 will not be restarted until approval is received from the IRB, DSMB, and FDA.

1395 In the absence of a device malfunction, use of the BP system by a participant will be
1396 discontinued if any of the following occur:

1397 The investigator believes it is unsafe for the participant to continue on the intervention.
1398 *This could be due to the development of a new medical condition or worsening of an
1399 existing condition; or participant behavior contrary to the indications for use of the
1400 device that imposes on the participant's safety*

1401 The participant requests that the treatment be stopped

1402 Participant pregnancy
1403 Two distinct episodes of DKA as defined in 9.2.4
1404 Two distinct severe hypoglycemia events as defined in section 9.2.3
1405 One episode of DKA as defined in 9.2.4 and one severe hypoglycemia event as defined in
1406 section 9.2.3
1407 Each DKA or severe hypoglycemia event will be reviewed by the Medical Monitor and by the
1408 DSMB with respect to determination of cause and whether the occurrence of the event can be
1409 attributed to use of the BP system.
1410 An additional requirement for continued system use following a single DKA or severe
1411 hypoglycemia event will be that (1) the site investigator believes that the event is explainable,
1412 unlikely to recur, and that it is safe for the participant to continue to use the system and (2) the
1413 Medical Monitor and DSMB concur. If either the Medical Monitor or DSMB determines that the
1414 occurrence of the event indicates that it is not safe for the participant to continue to use the BP
1415 system, use will be discontinued.

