1181 participant. A device complaint may occur independently from an AE, or along with an AE.
1182 An AE may occur without a device complaint or there may be an AE related to a device
1183 complaint. A device malfunction is any failure of a device to meet its performance specifications
1184 or otherwise perform as intended. Performance specifications include all claims made in the
1185 labeling for the device. The intended performance of a device refers to the intended use for
1186 which the device is labeled or marketed. (21 CFR 803.3). *Note: for reporting purposes, sites will
1187 not be asked to distinguish between device complaints and malfunctions.*

1188 9.2.2 Reportable Adverse Events

1189 For this protocol, a reportable adverse event includes any untoward medical occurrence that
1190 meets one of the following criteria:

- 1191 • An SAE
- 1192 • An ADE as defined in section 9.2.1, unless excluded from reporting in section 9.3
- 1193 • An AE as defined in 9.2.1 occurring in association with a study procedure
- 1194 • An AE as defined in 9.2.1 not related to a device issue which leads to temporary or
1195 permanent discontinuation of a study device
- 1196 • An AE as defined in 9.2.1 for which a visit is made to a hospital emergency department
- 1197 • Hypoglycemia meeting the definition of severe hypoglycemia as defined below
- 1198 • Diabetic ketoacidosis (DKA) as defined below or in the absence of DKA, hyperglycemia
1199 or ketosis event meeting the criteria defined below

1200 Hypoglycemia and hyperglycemia not meeting the criteria below will not be recorded as adverse
1201 events unless associated with an Adverse Device Effect. Skin reactions from sensor placement
1202 are only reportable if severe and/or required treatment.

1203 All reportable AEs—whether volunteered by the participant, discovered by study personnel
1204 during questioning, or detected through physical examination, laboratory test, or other means—

1205 will be reported on an AE form online. Each AE form is reviewed by the Medical Monitor to
1206 assess safety and to verify the coding and the reporting that is required.

1207 **9.2.3 Hypoglycemic Events**

1208 Hypoglycemia not associated with an Adverse Device Effect is only reportable as an adverse
1209 event when the following definition for severe hypoglycemia is met: the event required
1210 assistance of another person due to altered consciousness, and required another person to actively

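### The 24-hour reporting clock in protocol section 9.4 depends on the site's own relatedness call, so a severe hypoglycemia or DKA event called unrelated may be reported up to 7 days after site awareness, which does not fit sections 9.6 and 9.7

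*Protocol*

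**What the plan says.** **Reporting clocks (protocol 9.4, Timing of Event Reporting).** The fast track reads "SAEs possibly related to a study device or study participation and UADEs must be reported to" "the Coordinating Center within 24 hours of the site becoming aware of the event". For the remaining ADEs and AEs, the section says "other reportable AEs should be submitted by completion on the on line form within 7 days of the" site learning of the event.

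**Status of the two events (9.2.2 to 9.2.4).** Section 9.2.2 lists as reportable "Hypoglycemia meeting the definition of severe hypoglycemia as defined below", and lists DKA separately, with no relatedness condition on either. Sections 9.2.3 and 9.2.4 treat both as SAEs for reporting purposes.

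**Who judges cause (9.2.5, 9.2.8).** The site investigator first classifies the event as related or not. The Medical Monitor then reviews that judgment and "will have the final say in determining the causality as well as whether an event is classified as a" serious adverse event.

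**Oversight (9.6).** The DSMB is to be "informed of all cases of severe hypoglycemia and diabetic ketoacidosis irrespective of device" relationship, when the events happen. The Medical Monitor typically reviews an SAE within 24 hours, counted from the report.

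**Continued use (9.7).** The Medical Monitor and the DSMB review each severe hypoglycemia or DKA event for cause. The section then sets "An additional requirement for continued system use following a single DKA or severe" hypoglycemia event: the site investigator must consider continuation safe, and the Medical Monitor and DSMB must agree.

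**The concern.** Sections 9.6 and 9.7 deliberately ignore the site's view of cause. Every severe hypoglycemia or DKA event goes to the DSMB, and central review is there to establish cause. Section 9.4 works the other way: the site's view of cause decides whether the central reviewers are owed a report in one day or in seven. The judgment under review thus controls the timing of the review.

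What is at stake is participant protection and the DSMB's ability to act on single events. In the BP groups, two parties must agree before use continues, yet for an event called unrelated the reporting rule does not ensure that they hear of it promptly. The DSMB notice in 9.6 is not limited to BP users, so control events called unrelated fall under the 7-day limit as well.

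No endpoint or safety count is affected. A late report is still a report, and the event still enters the safety tabulations in protocol 11.7 and SAP section 10.

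**Working it through.** The plan gives no figure of its own here. The check is a comparison of the sections plus arithmetic on their time limits.

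1. **Does SAE status start the 24-hour clock?** Under 9.2.3 and 9.2.4, severe hypoglycemia and DKA are SAEs. Section 9.4 names two entry routes to the fast track: UADE status, or an SAE possibly related to a study device or to participation. SAE status alone is neither. An event called unrelated therefore falls to the residual category of reportable AEs.

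2. **The two limits, from site awareness (9.4).**
   - Possibly related: 24 hours.
   - Called unrelated: 7 × 24 = 168 hours.
   - Difference: 168 − 24 = 144 hours, or 6 days.

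3. **Time to first central review**, adding the typical 24-hour Medical Monitor review after the report (9.6).
   - Possibly related: 24 + 24 = 48 hours, about 2 days.
   - Called unrelated: 168 + 24 = 192 hours, about 8 days.
   - These are upper ends of what 9.4 allows, not expected times.

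4. **Compare with 9.6.** Notice to the DSMB covers all cases, has no relatedness filter, and is tied to the event's occurrence. It is contrasted with compiled review at intervals. A 168-hour allowance for part of the same set of events does not match.

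5. **Compare with 9.7.** This section gives no number of hours. What it adds is that each event is reviewed for cause and that agreement is a condition of continued BP use after one event. Both steps need the report first.

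6. **Does another clause close the gap?**
   - Section 9.1 asks for prompt reporting of unanticipated problems, but only those that are unexpected and related or possibly related.
   - Protocol 11.7 and SAP section 10 mention real-time reporting of certain events in the BP Group. Section 9.4 has no such provision for severe hypoglycemia or DKA called unrelated.
   - Section 9.4 speaks of possible relatedness, while 9.2.5 offers only yes or no, so the boundary between the two clocks is itself loosely defined.

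**The case against.** The best defense has four parts.

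- **The limit is a maximum.** A site that reports on day 1 complies with 9.4, 9.6 and 9.7 together. This stands: the sections can all be met. It does not answer the point that 9.4 permits the lag.
- **Few events may be called unrelated.** The test in 9.4 includes study participation. Section 9.2.5 allows a yes when the event follows a known response pattern, and hypo- and hyperglycemia are listed risks in 1.4.1. This narrows the route. It does not close it, since 9.2.5 also supports a no where intercurrent illness or another cause explains the event.
- **Other text protects the participant.** DKA by definition is treated in a health care facility (9.2.4). Under 4.3, a hospitalized participant is told to contact staff and stop the iLet, and one unable to eat for more than a day must notify staff. This covers some DKA. It does not cover severe hypoglycemia treated at home or emergency care without admission, and it does not shorten the step from site to Coordinating Center.
- **DSMB details are in a separate document (9.6).** It is not available here and may contain a faster route. If so, 9.4 should still agree with it.

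A reader might go further and infer two things that the documents do not support. First, that a device malfunction without harm has no deadline. Section 9.7 pauses BP use for a malfunction leading to such an "event (or a malfunction that could have led to severe hypoglycemia or DKA), use of the BP" system being suspended, and its next sentence calls this the UADE. Section 9.4 puts UADEs on the 24-hour clock, and the definition in 9.2.1 extends to serious device problems without an adverse event. Second, that a second event could slip past the two-event rule. That rule in 9.7 operates without central review of the first event.

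**Conclusion.** The inconsistency is real and is confined to the reporting clock. For a severe hypoglycemia or DKA event called unrelated by the site, 9.4 allows 168 hours where a related event has 24. That allowance fits neither the all-cases notice in 9.6 nor the review and agreement in 9.7. The site's provisional causality call should not decide how quickly those with authority over causality learn of the event.

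Three limits apply to the conclusion:

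- Section 9.7 sets no deadline. It would be wrong to say that the stopping rules demand immediate review; the timing language is in 9.6, and it states no hours.
- It would also be wrong to conclude that a participant may stay on the device for a week. A form deadline is not permission to continue, and 9.7 makes agreement a condition of continued use.
- The number of events affected cannot be estimated. The documents give no expected count of severe hypoglycemia or DKA, nor of the share that sites would call unrelated. The 144-hour difference is the only supportable measure of size.

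The verdict assumes that 9.4 is applied as written and that the separate DSMB document sets no shorter site deadline. The change is worth making because it is cheap and serves participant safety; it is not a threat to the trial's statistical conclusions.

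**What to change.** Amend 9.4 so that every severe hypoglycemia and DKA event is reported to the Coordinating Center within 24 hours of site awareness, whatever the site's relatedness call. Extending this to every SAE is simpler to state and to train.

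The sponsor should also reconcile 9.4, 9.6 and 9.7 on what applies between a first event and the agreement of the Medical Monitor and DSMB. That is a clinical rule for the sponsor to set, and none is proposed here.

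The cost is one sentence of protocol text, brief site retraining, and a few more expedited reports. The forms, the Medical Monitor review and the DSMB pathway already exist.

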9.7.1 Criteria for Suspending or Stopping Overall Study

1416 In addition to the suspension of device use due to a UADE as described in 9.7, study activities
1417 could be similarly suspended if the manufacturer of any constituent study device requires
1418 stoppage of device use for safety reasons (e.g. product recall). The affected study activities may
1419 resume if the underlying problem can be corrected by a protocol or system modification that will
1420 not invalidate the results obtained prior to suspension.
1421
1422 The Medical Monitor or the DSMB may request suspension of study activities or stoppage of the
1423 study if deemed necessary based on the totality of safety data available.

1424

Chapter 10: Miscellaneous Considerations

1425

10.1 Collection of Medical Conditions and Medications

1426

Pre-Existing Conditions: Collection of pre-existing conditions will include any medical condition that is either present at screening, a chronic disease, or a prior condition that could impact the participant's health during the course of the study (e.g., prior myocardial infarction or stroke).

1430

Medical Conditions during the study: The following medical conditions that do not qualify for reporting on an Adverse Event Form should be reported on the Medical Conditions Form: (1) new diagnosis of a chronic disease (i.e., not present at the time of enrollment) and (2) any medical condition that could affect the participant's ability to carry out any aspect of the protocol or could affect an outcome assessment. Transient conditions that do not affect the participant's ability to carry out the protocol or study data related to any study outcome do not need to be reported.

1437

Medications: All medications that the participant is currently taking at screening and during the course of the study should be recorded. Nutraceuticals and preventative treatment also should be recorded. This will include the treatment of chronic pre-existing conditions, medical conditions that occur during the study (both reportable and not-reportable medical conditions), and/or adverse events. Medications only taken as needed either can be recorded when prescribed or only recorded if used during the study. Glucagon for treatment of severe hypoglycemia will only be recorded if used during the study.

1444

